15.1.2.32 Section 10.3.2.3 Analysis of safety variables

This section was changed as a result of Modification 15.1.1.15 and 15.1.1.26.

Old text:

All safety variables will be analyzed based on the SAF.

The main safety variable is the incidence of ~~post-baseline~~ adverse events (both serious and non-serious).

New text:

All safety variables will be analyzed based on the SAF.

The main safety variable is the incidence of treatment-emergent adverse events (both serious and non-serious). Treatment-emergent AEs are defined as any AEs occurring during the 'extension treatment period' starting at Day 1 of Year 6 of Mirena use.

15.1.2.33 Section 10.3.2.3.2 Bleeding pattern

This section was changed as a result of Modification 15.1.1.10, 15.1.1.19 and 15.1.1.26.

Old text:

Bleeding diary data will be analyzed according to the sponsor's Best practice entitled "Recording and evaluation of bleeding data".

[...]

Table 10–2 Bleeding Intensity Codes and WHO Definitions for Bleeding Intensity

Bleeding Intensity Codes		WHO Definitions
3 - 5	Bleeding/spotting episode:	Day(s) with bleeding/spotting preceded and followed by at least 2 bleeding-free days.
2	Spotting-only episode:	Day(s) with spotting preceded and followed by at least 2 bleeding-free days.
1	Bleeding/spotting-free interval:	At least 2 days without bleeding/spotting preceded and followed by at least 1 bleeding/spotting day.

[...]

Based on daily data obtained from the electronic diary, the bleeding pattern will be reported using reference periods of 28 and 90 days. The first 28-day and 90-day reference period, respectively, will start at ~~the baseline visit (Visit 2)~~. For each subject and for each period, the number of bleeding/spotting days and bleeding/spotting episodes will be calculated.[...]

New text:

Bleeding diary data during the ‘extension treatment period’ starting at Day 1 of Year 6 of Mirena use will be analyzed according to the sponsor’s Best Practice Document entitled “Recording and evaluation of bleeding data”. Bleeding diary data prior to the ‘extension treatment period’ will not be included in the analyses. The handling of partial or missing data and detailed imputation rules will be described in the statistical analysis plan.

[...]

Table 10–2 Bleeding Intensity Codes and WHO Definitions for Bleeding Intensity – amended

Bleeding Intensity Codes		WHO Definitions
2 - 5	Bleeding/spotting episode:	Day(s) with bleeding/spotting preceded and followed by at least 2 bleeding-free days.
2	Spotting-only episode:	Day(s) with spotting preceded and followed by at least 2 bleeding-free days.
1	Bleeding/spotting-free interval:	At least 2 days without bleeding/spotting preceded and followed by at least 1 bleeding/spotting day.

[...]

Based on daily data obtained from the electronic diary, the bleeding pattern will be reported using reference periods of 28 and 90 days. The first 28-day and 90-day reference period,

respectively, will start at Day 1 of Year 6 of Mirena use. For each subject and for each period, the number of bleeding/spotting days and bleeding/spotting episodes will be calculated. [...]

15.1.2.34 Section 10.5 Planned interim analyses

This section was changed as a result of Modification 15.1.1.1.

Old text:

No formal interim analysis in the sense of a group sequential or adaptive design is planned. However, an analysis of the data is planned after year 7, including all subjects who have prematurely discontinued or completed Visit 6, i.e. treated with Mirena for up to 7 years (2 years in the study).

New text:

No formal interim analysis in the sense of a group sequential or adaptive design is planned. However, an analysis of the data is planned after Year 6, including all subjects who have prematurely discontinued or completed Visit 4, i.e. treated with Mirena for up to 6 years (1 year in the study). Another analysis of the data is planned after Year 7, including all subjects who have prematurely discontinued or completed Visit 6, i.e. treated with Mirena for up to 7 years (2 years in the study).

15.1.2.35 Section 11.1 Data recording

This section was changed as a result of Modification 15.1.1.23.

Old text:

The data collection tool for this study will be eCRF; a validated electronic data capture system called RAVE. Subject data necessary for analysis and reporting will be entered/transmitted into a validated database or data system (CIE/TOSCA; SAS).

~~Covance will perform the data entry for this study.~~ Data will be entered by site personnel into an internet based electronic data capture software system RAVE, which Covance has licensed from Medidata Solutions Worldwide. RAVE has been validated by Medidata Solutions Worldwide and Covance for use in its clinical studies. [...]

New text:

The data collection tool for this study will be eCRF; a validated electronic data capture system called RAVE. Subject data necessary for analysis and reporting will be entered/transmitted into a validated database or data system (e.g. CIE/TOSCA; SAS).

Data will be entered by site personnel into an internet based electronic data capture software system RAVE, which Covance has licensed from Medidata Solutions Worldwide. RAVE has

been validated by Medidata Solutions Worldwide and Covance for use in its clinical studies.
[...]

15.1.2.36 Section 13.1 Investigators and other study personnel

New text added:

The name and contact information for the Sponsor's Study Medical Expert is provided in Section 1. The co-ordinating investigator who will be responsible for signing the CSR, is PPD (study center #^{PPD} All other study personnel not included in this section are identified in a separate personnel list (not part of this clinical study protocol) as appropriate. [...]

SHBG	Sex hormone binding globulin
SOC	System organ class
TVUS	Transvaginal ultrasound
WHO	World Health Organization

1. Introduction

Mirena, a levonorgestrel-releasing intrauterine system (LNG IUS; initial in vitro release rate 20 µg LNG / day), has been proven a safe and reliable method of contraception over the 5 years of labeled use. It has been on the market since the mid-1990s in most European countries and since 2001 in the US.

This study will evaluate the contraceptive efficacy of Mirena during extended use for up to 8 years. The stability of the effect on heavy menstrual bleeding (HMB) during extended use will be studied in a subgroup of women for whom Mirena was prescribed for HMB (as a secondary indication to contraception).

The Statistical Analysis Plan (SAP) is based on the Integrated Protocol v2.0 (dated 20 SEP 2017), and describes the analysis planned after Year 6, the analysis planned after Year 7 and the final analysis after 8 years of extended use of Mirena. Further details about the analysis planned after Year 6 and Year 7, respectively, are given in Section 4.6.

The SAP v3.0 (supplement) describes post-hoc analyses planned after the Year 6 database lock. The SAP v4.0 (supplement) describes clarifications/corrections and additions, introduced prior to Year 7 database lock. All changes/additions are summarized in the document history in Section 7.

2. Study Objectives

Primary objective of the study is to assess the contraceptive efficacy of Mirena beyond 5 years and up to 8 years of use.

[figure not shown]
Secondary objectives for the study are the assessment of menstrual blood loss (in women that had Mirena inserted for the indication HMB) and safety.

Further objectives are the population pharmacokinetic evaluation of LNG plasma concentration data and evaluation of user satisfaction.

3. Study Design

This is a multi-center, open-label, uncontrolled, single group study to be conducted in the US only. Study design is presented below in [Figure 3-1](#).

Figure 3–1 Overview of the Study Design

The target for the total number of women to be included in the extended treatment period is 360 women (200 women to complete study treatment). To evaluate the effect of extended Mirena use on HMB, it is targeted that 10% of the women to be treated (i.e. 36 women out of 360) should have Mirena prescribed for the treatment of HMB in addition to contraception. Please note subjects who have Mirena prescribed for contraception and HMB will have to consent to the HMB subgroup procedures.

The study will consist of a screening, treatment, and a follow-up period. Screening can be started when the subject has had the Mirena in place for 4 years and 6 months. Screening activities should be completed within 60 days after signed informed consent to allow enough time for the evaluation of the subjects’ eligibility to the study. Baseline visit (Visit 2) will be scheduled to take place 0 to 14 days before the end of Year 5 of Mirena use; and this is the start of the ‘treatment period’. The ‘treatment period’ is defined as the 3-year period following the baseline visit, whereas the ‘extension treatment period’ is defined as the 3-year period following Day 1 of Year 6 of Mirena use, i.e. Years 6, 7 and 8 of extended use of Mirena (refer to Section 4.1.1 for further details).

Analyses of the efficacy and safety data will be conducted after all subjects have either completed 6 and 7 years of treatment, respectively, or prematurely terminated their study participation before this time point.

Final analysis will be done after all subjects have either completed 8 years of treatment or prematurely terminated their study participation.

4. General Statistical Considerations

4.1 General Principles

The statistical evaluation will be performed by using the software package SAS release 9.2 or higher (SAS Institute Inc., Cary, NC, USA). All variables will be analyzed by descriptive statistical methods. The number of data available and missing data, mean, standard deviation, minimum, quartiles, median, and maximum will be calculated for metric data. Mean, standard deviation, quartiles and median will be presented with one more decimal place than raw data; minimum and maximum will be presented with the same number of decimal places like raw data. Frequency tables will be generated for categorical data.

Summary tables on disposition and demographics will be displayed with three columns:

- Subjects in HMB subgroup, i.e. indication “Contraception and HMB”
- Subjects not in HMB subgroup, i.e. indication “Contraception”
- Total subjects

Summary tables on study drug administration, efficacy, safety and pharmacokinetics will be displayed with one column:

- Total subjects

4.1.1 ‘Treatment Period’ versus ‘Extension Treatment Period’

In order to allow some flexibility, the baseline visit is planned to take place 0 to 14 days before the end of Year 5 of Mirena use (see Integrated Protocol Table 9–1); and this is the start of the ‘treatment period’. The ‘extension treatment period’ will start at Day 1 of Year 6 of Mirena use. As a consequence of the visit window, it is expected there will be various subjects with this baseline visit taking place prior to the start of the ‘extension treatment period’. Please also refer to Section 4.7.

The following variables, collected on an ongoing basis, will primarily be analyzed for the ‘extension treatment period’ starting at Day 1 of Year 6 of Mirena use, i.e., data collected between the baseline visit and Day 1 of Year 6 of Mirena use will be excluded:

- Primary efficacy variable, i.e. occurrence of pregnancies (Section 6.2.1)
- Main safety variable, i.e. adverse events (Section 6.4.2)
- Uterine bleeding / bleeding pattern (Section 6.4.3)

The following variables, collected at pre-specified visits/timeframes only, will be analyzed per visit (unless otherwise stated):

- Secondary efficacy variable, i.e. menstrual blood loss (Section 6.2.2)
- Other safety variables, not listed above (Sections 6.4.4, 6.4.5, 6.4.6)
- Other variables (Section 6.4.6.6)

4.2 Handling of Dropouts

Depending on the time point of withdrawal, a withdrawn subject is referred to as either a “screening failure” or “dropout”. A subject who discontinues study participation prematurely for any reason is defined as a “dropout” if the subject has already been deemed eligible to participate and has completed the baseline visit. A subject who terminates the study before completion of the baseline visit is regarded a “screening failure”.

Dropouts are not to be replaced.

4.3 Handling of Missing Data

All missing or partial data will be presented in the subject data listing as they are recorded on the Case Report Form (CRF) and the Bleeding Diary, respectively.

Date Mirena last known in situ (as defined in Section 4.7)

- If the day of the month of the date when Mirena threads were visible is missing, it will be imputed as the 15th of that month.
- If the date when Mirena threads were visible is missing (after possible imputation of a missing day), the date of Day 1 Year 6 will be used instead.
- If the day of the month of the date when Mirena location was found to be “In situ” or “Displaced, intrauterine” is missing, it will be imputed as the 15th of that month.
- If the date when Mirena location was found to be “In situ” or “Displaced, intrauterine” is missing (after possible imputation of a missing day), the date of Day 1 Year 6 will be used instead.

Stop date of study drug administration (as defined in Section 4.7)

- If the day of the month of the Mirena expulsion/removal date is missing and the subject was *not* pregnant during the extension treatment period, it will be imputed as the 15th of that month of Mirena expulsion/removal.
- If the day of the month of the Mirena expulsion/removal date is missing and the subject *was* pregnant during the extension treatment period, it will be imputed as follows:
 - If the subject was confirmed to be pregnant during that month (i.e. estimated date of conception during that month), the day of Mirena expulsion/removal will be imputed by the estimated day of conception.
 - If the subject was confirmed to be pregnant prior to that month (i.e. estimated date of conception prior to that month), the day of the Mirena expulsion/removal will be imputed by the first of that month of Mirena expulsion/removal.

- If the subject was confirmed to be pregnant after that month (i.e. estimated date of conception after that month), the day of the Mirena expulsion/removal will be imputed by the last of that month of Mirena expulsion/removal.
- If the Mirena expulsion/removal date is missing (after possible imputation of a missing day), the ‘date Mirena last known in situ’ will be used instead.

eDiary data

Missing bleeding diary data will be imputed following the sponsor’s Best Practice Document (BPD) on “Recording and Evaluation of Bleeding Data” (RD-SOP-1107) (1) and as described in Section 4.4, respectively.

Adverse event (AE) data

The onset date of AEs is needed to distinguish treatment-emergent and pretreatment AEs. If the day of the month is missing, the last day of that month will be used for the derivations of the treatment emergent flag. If both day and month are missing December 31st will be used. Using this approach, AEs will always considered to be treatment emergent unless this can be ruled out.

Furthermore, the onset date of AEs is needed to distinguish between AEs in 6th / 7th / 8th year. If the day of the month is missing, the 15th of that month will be used for calculation of the year of onset. If both day and month are missing, July 1st will be used. If an upper or lower bound for the date is available (e.g. Day 1 Year 6), this date will be taken into account.

Pregnancy data: Pearl index (PI) calculation and cumulative failure rate

- Partially missing conception dates will be imputed by the minimum approach, i.e. the first possible on-treatment date (Day 1 Year 6) will be used.
- If the day of the month of the Mirena expulsion/ removal date is missing, it will be imputed as the 15th of that month.
- If the Mirena expulsion/ removal date is missing (after possible imputation of a missing day), the ‘date Mirena last known in situ’ will be used instead.

Time to expulsion/ perforation/ non-compliance

- If the day of the month of the date of expulsion/ perforation/ non-compliance is missing, it will be imputed as the 15th of that month.
- If the date of expulsion/ perforation/ non-compliance is missing (after possible imputation of a missing day), the ‘date Mirena last known in situ’ will be used instead.

Time to premature discontinuation

- If the day of the month of the date of premature discontinuation of study treatment is missing, it will be imputed as the 15th of that month.
- If the date of premature discontinuation of study treatment is missing (after possible imputation of a missing day), the date of the subject’s last scheduled or unscheduled visit prior to the end of treatment visit will be used.

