10.4 Determination of sample size

The sample size calculation is not based on statistical considerations. It is targeted to have 200 women completing the 8th year of treatment with Mirena. With an estimated dropout rate of 15%, the total number of women to be enrolled into the study treatment phase would be 350.

In order to account for women excluded from the primary analysis due to age restrictions (i.e. women 34 years of age at baseline or older will not be included in the primary analysis set 'PAS year 8' for the final analysis after 8 years)², the total number of women to be enrolled into the study treatment phase is 360.

² It is assumed about 90% of women enrolled will be 18 to 32 years of age at screening, i.e. 10% of women will be 33 to 35 years old and accordingly less will be 34 to 35 years old.

Sample size characteristics regarding the analysis of the Pearl index:

This sample size will lead to an expected exposure (years 6 to 8 combined) of 832 women years (WY). Assuming a true Pearl index of 0.2,

- the upper limit of the 95% confidence interval for the PI (years 6-8) will not exceed 1 with a probability of 76%,
- the difference between the point estimate and the upper limit of the 95% confidence interval will not exceed 1 with a probability >99.9%.

Assuming a slightly higher true Pearl index of 0.3,

- the upper limit of the 95% confidence interval for the PI (years 6-8) will not exceed 1 with a probability of 55%,
- the difference between the point estimate and the upper limit of the 95% confidence interval will not exceed 1 with a probability >99.9%.

CCI

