The exact rules regarding how the crude exposure time will be calculated are given in Integrated Protocol Section 10.3.2.1 and Integrated Protocol Table 10–1 as well as in [Table 6–1](#) below.

Table 6–1: Definition of crude exposure times

PI	Reason for end of study/ continuation status	Crude exposure time
1-year PI (6th year)	Total expulsion	Date, when expulsion was discovered – Date of Day 1 Year 6 +1
	Partial Expulsion/ Mirena removal	Date of Mirena removal – Date of Day 1 Year 6 +1
	Pregnancy	Date of conception – Date of Day 1 Year 6 +1
	Lost to Follow-up	Maximum of (Date Mirena last known in situ – Date of Day 1 Year 6 +1; 1 day)
	Continues into 7th year of treatment	365 days
2-year PI (6th and 7th year)	Total expulsion	Date, when expulsion was discovered – Date of Day 1 Year 6 +1
	Partial Expulsion/ Mirena removal	Date of Mirena removal – Date of Day 1 Year 6 +1
	Pregnancy	Date of conception – Date of Day 1 Year 6 +1
	Lost to Follow-up	Maximum of (Date Mirena last known in situ – Date of Day 1 Year 6 +1; 1 day)
	Continues into 8th year of treatment	730 days
3-year PI (6th, 7th and 8th year)	Total expulsion	Date, when expulsion was discovered – Date of Day 1 Year 6 +1
	Partial Expulsion/ Mirena removal	Date of Mirena removal – Date of Day 1 Year 6 +1
	Pregnancy	Date of conception – Date of Day 1 Year 6 +1
	Lost to Follow-up	Maximum of (Date Mirena last known in situ – Date of Day 1 Year 6 +1; 1 day)
	Continues into 9th year of treatment	Minimum of (1095 days; Date of EOT visit – Date of Day 1 Year 6 +1)
Overall PI	Total expulsion	Date, when expulsion was discovered – Baseline visit date +1
	Partial Expulsion/ Mirena removal	Date of Mirena removal – Baseline visit date +1
	Pregnancy	Date of conception – Baseline visit date +1
	Lost to Follow-up	Maximum of (Date Mirena last known in situ – Baseline visit date +1; 1 day)
	Continued until EOT	Date of EOT visit – Baseline visit date +1

PI=Pearl Index; EOT=End of treatment

A pregnancy will be allocated to the time period(s) that are relevant for the calculation of the PIs described above, e.g., a pregnancy that occurs on day 400 will be relevant for the 7th year PI, the 2-year PI (6th & 7th year), the 3-year PI (6th, 7th & 8th year), and the overall PI. Pregnancies that occur before Day 1 Year 6 of Mirena use will not count for the 1-year PI, 2-year PI and 3-year PI. Pregnancies that occur after the Mirena was removed or an expulsion was discovered will not count for any PI calculation.

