To assess pregnancies with regard to subgroup combinations, e.g. by age and parity, a listing on all pregnancies providing detailed information regarding subject number, age, parity, date of Mirena insertion, date of baseline visit, date of Day 1 Year 6 of Mirena use, date of Mirena removal, (estimated) date of (partial/total) expulsion, estimated date of conception, location of pregnancy implantation at time of diagnosis, and estimated date of conception relative to Mirena insertion/ relative to Day 1 Year 6 of Mirena use/ relative to stop date of study drug administration will be provided.

Secondary analysis:

In order to fulfill the European guideline EMEA-‘Guideline on clinical investigation of steroid contraceptives in women’ (EMEA/CPMP/EWP/519/ Rev1, July 2005.) (2), the cumulative failure rate, i.e. the probability of getting pregnant will be calculated using the Kaplan-Meier method in addition to calculation of the different PIs.

Periods of backup contraception use will not be subtracted from the exposure time.

Sensitivity analysis:

The usual assumption for the calculation of the PI is a constant hazard for the event of becoming pregnant over time. As this cannot necessarily be assumed for the study treatment of this study, PIs will be calculated *per year*, as sensitivity analyses.

Similar analyses (PIs and cumulative failure rates) will be provided for ectopic pregnancies.

Sensitivity analysis (introduced post-hoc after Year 6 database lock, prior to Year 7 database lock):

The primary analysis (‘1 year PI (sixth year)’ after Year 6 database lock based on the PAS Year 6) was conducted using the following rules:

- 1 WY = 365 days
- Complete and incomplete 28-day cycles are used for the exposure calculation (i.e., the days of the last 28-day cycle are used even if incomplete)

A sensitivity analysis will be conducted using the following rules

- 1 WY = 13 28-day cycles (i.e., 364 days)
- Only complete 28-day cycles are used

Similar analyses will be performed after Year 7 and Year 8 database lock, i.e. ‘2 year PI (sixth and seventh year)’ after Year 7 database lock based on the PAS Year 7 and ‘3 year PI (sixth, seventh and eighth year)’ after Year 8 database lock based on the PAS Year 8, respectively. PIs will be also be calculated *per year*, i.e. ‘Year 6 PI’ and ‘Year 7 PI’ after Year 7 database lock based on the PAS Year 7 and ‘Year 6 PI’, ‘Year 7 PI’ and ‘Year 8 PI’ after Year 8 database lock based on the PAS Year 8.

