As for the primary analysis, pregnancies that occur within 7 days after the end of exposure as well as pregnancies that occur after partial expulsion or first occurrence of non-compliance

but before Mirena removal will count for the PI calculations; 28-day reference period(s) of backup contraception use will be excluded from the exposure time.

Repeated analysis of the primary efficacy variable (introduced prior to Year 8 database lock) for the PAS Year 6 and PAS Year 7 based on the final database after Year 8:

For the analysis after 6 years of Mirena use, the primary efficacy variable was the occurrence of pregnancy within year 6 of Mirena use (i.e. ‘1-year PI’) based on the PAS Year 6, which was analysed based on the interim database after Year 6 and reported in the Year 6 CSR.

For the analysis after 7 years of Mirena use, the primary efficacy variable was the occurrence of pregnancy within years 6 through 7 of Mirena use (i.e. ‘2-year PI’) based on the PAS Year 7, which was analysed based on the interim database after Year 7 and reported in the Year 7 CSR.

These analyses (and the corresponding sensitivity analyses) will be repeated after the final database lock, to provide these results based on the most accurate and complete datasource, i.e. the final database after Year 8:

- For the PAS Year 6, based on the final database after Year 8:
 - ‘1-year PI’ (Year 6)
 - ‘1-year PI’ (Year 6) – based on only complete 28-day cycles
 - ‘1-year PI’ (Year 6) – for ectopic pregnancies
 - ‘1-year probability of getting pregnant’ (Year 6)
 - ‘1-year probability of getting pregnant’ (Year 6) – for ectopic pregnancies
- For the PAS Year 7, based on the final database after Year 8:
 - ‘2-year PI’ (Years 6 and 7) and PIs calculated *per year*, i.e. ‘Year 6 PI’ and ‘Year 7 PI’
 - ‘2-year PI’ (Years 6 and 7) and PIs calculated *per year*, i.e. ‘Year 6 PI’ and ‘Year 7 PI’ – based on only complete 28-day cycles
 - ‘2-year PI’ (Years 6 and 7) and PIs calculated *per year*, i.e. ‘Year 6 PI’ and ‘Year 7 PI’ – for ectopic pregnancies
 - ‘2-year probability of getting pregnant’ (Years 6 and 7) and probabilities calculated *per year*, i.e. ‘Year 6 probability of getting pregnant’ and ‘Year 7 probability of getting pregnant’
 - ‘2-year probability of getting pregnant’ (Years 6 and 7) and probabilities calculated *per year*, i.e. ‘Year 6 probability of getting pregnant’ and ‘Year 7 probability of getting pregnant’ – for ectopic pregnancies

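### SAP 4.3 dates every partly known conception to Day 1 of Year 6, which moves late failures into Year 6 and lowers the Kaplan-Meier failure rate

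*SAP*

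**What the plan says.** In SAP section 4.3, the pregnancy-data rules cover both the PI and the cumulative failure rate. They state: "Partially missing conception dates will be imputed by the minimum approach, i.e. the first possible on-treatment date (Day 1 Year 6) will be used". There is no separate branch for a date whose month and year are recorded.

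The adverse-event rule in the same section works differently. For the year of onset, "If the day of the month is missing, the 15th of that month will be used for calculation of the year of onset", and "If an upper or lower bound for the date is available (e.g. Day 1 Year 6), this date will be taken into account". The rules for a missing day of removal, expulsion, perforation or discontinuation also keep the recorded month.

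SAP section 6.2.1 then relies on the conception date in several places:

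- Allocation to a treatment year. Its example is that "a pregnancy that occurs on day 400 will be relevant for the 7th year PI".
- Exposure. In Table 6-1, a pregnancy contributes conception date minus Day 1 Year 6, plus 1 day.
- Per-year PIs, because the PI presumes a constant hazard: "As this cannot necessarily be assumed for the study treatment of this study, PIs will be calculated" per year.
- The secondary analysis, in which "the probability of getting pregnant will be calculated using the Kaplan-Meier method".
- The 1-year PI (PAS Year 6) and 2-year PI (PAS Year 7): "These analyses (and the corresponding sensitivity analyses) will be repeated after the final database lock".

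Section 4.3 also has two rules for a missing removal day in a pregnant woman. If conception fell in the removal month, the stop-date rule uses the day of conception, while the PI rule uses the 15th.

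**The concern.** The per-year PIs exist to show whether failure rises as the device ages. A rule that moves late failures to the start of Year 6 works against that purpose: Years 7 and 8 look better than they were and Year 6 looks worse. The Kaplan-Meier estimate is lowered because the event is placed where the risk set is largest. The re-run 1-year PI can gain a pregnancy conceived in Year 7 or 8, and the re-run 2-year PI one conceived in Year 8. SAP 6.2.1 tells readers to expect only minor changes in these re-runs, caused by more complete exposure.

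The SAP's own day-400 case shows the problem. If only the day of the month were missing, that 7th-year pregnancy would become a Year 6 pregnancy with 1 day of exposure instead of 400.

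The removal-day mismatch is a smaller matter. Under the PI rule, a conception later in the month than the imputed removal plus 7 days drops out of every PI, even if the device was still in place.

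**Working it through.** **Inputs.** Protocol 10.4 gives 350 women (before the increase to 360 for age), 15% dropout, 832 woman-years (WY) over Years 6-8, and true PIs of 0.2 and 0.3. SAP 6.2.1 gives exact Poisson limits: lower 0.5·χ²(0.025, 2x)/E and upper 0.5·χ²(0.975, 2(x+1))/E, with E in 100 WY.

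**1. Reproduce the plan's exposure.** At 15% loss per year, the numbers at risk at the start of Years 6, 7 and 8 and the end of Year 8 are 350, 297.5, 252.9 and 214.9. Mid-year averages give 323.75 + 275.19 + 233.91 = 832.85 WY, which matches 832. Reading 15% as the total over three years gives 971 WY, which does not. The split by year is therefore an assumption; the protocol states only the total.

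**2. Expected events.** 0.2 × 8.32 = 1.7 and 0.3 × 8.32 = 2.5 pregnancies over the whole study, so a single partial date can settle a per-year result.

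**3. One Year 8 failure with month and year known and day missing.**

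| Result | Rule as written | Recorded month kept |
|---|---|---|
| Year 6 PI | 1/3.2375 = 0.31 (0.01-1.72) | 0 (upper 1.14) |
| Year 8 PI | 0 (upper 1.58) | 1/2.339 = 0.43 (0.01-2.38) |
| 2-year PI | 1/5.989 = 0.17 (0.00-0.93) | 0 (upper 0.62) |
| Kaplan-Meier failure to end of Year 8 | 1/350 = 0.29% | 1/252.9 to 1/214.9 = 0.40-0.47% |

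The PI rows leave out the small exposure loss. Including it for a conception on day 900 changes the Year 6 upper limit from 1.72 to 1.73. The relative Kaplan-Meier understatement runs from 1 − 252.9/350 = 28% to 1 − 214.9/350 = 39%.

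**4. Other attrition.** At 10% per year (332.5, 299.2 and 269.3 WY), the Year 6 PI is 0.30 instead of 0 and the Year 8 PI is 0 instead of 0.37. At 20% (315.0, 252.0 and 201.6 WY), they are 0.32 instead of 0 and 0 instead of 0.50. These rates give totals of 901 and 769 WY, so they bracket the plan's figure.

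**5. Primary 3-year PI.** One moved pregnancy loses at most 1,094 days, or 3.0 WY. With two pregnancies and one moved, 2/8.32 = 0.2404 becomes at most 2/8.29 = 0.2413, a rise of 0.36%.

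**6. Removal-day mismatch.** Under the PI rule, the 15th plus 7 days is the 22nd, so a conception after the 22nd of the removal month is not counted. Take conception on 25 May and removal in May on an unknown day. Under the 7-day rule the pregnancy should count if removal was on or after 18 May. Exclusion is therefore right for 1-17 May (17 of 31 days) and wrong for 18-31 May (14 of 31).

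**The case against.** - **The wording may intend something narrower.** A minimum approach could mean the earliest date compatible with what is recorded, with Day 1 Year 6 as a floor. The stop-date rule does use the month of conception. However, the text names one fixed date in parentheses, and a programmer would code that date. If the narrower reading was meant, the sentence still needs changing.
- **The primary result hardly changes.** This stands. The affected results are sensitivity, secondary and repeated analyses. For the Year 6, 1-year and 2-year PIs the shift counts against the product; only the Year 7 and 8 PIs and the 3-year Kaplan-Meier rate are flattered.
- **The harm is conditional and small in absolute terms.** This also stands. Protocol 9.4.1.1 asks for the conception date to be estimated where it can be, so most dates may be complete. The Kaplan-Meier gap is 0.11-0.18 percentage points on one event, and a one-event 95% log-log interval around 0.43% runs from about 0.06% to 3.0%.
- **Table 6-1 might override the rule in the re-runs.** A woman who continued into Year 7 also fits the row that gives 365 days. That affects only the denominator. The pregnancy would still be allocated by its imputed date, and the PI stays at about 0.31.
- **Listings would reveal a shift.** Partial dates are listed as recorded, and SAP 6.2.1 plans a pregnancy listing. The tables would still follow the rule.
- **A late change is post hoc.** Year 6 and Year 7 results have already been reported. This calls for a dated, documented change and a note of any effect on comparability. The SAP already has supplements dated before the Year 7 and Year 8 database locks.
- **The removal-day case is rare.** Agreed. It is worth settling only because two rules in one section give different dates.

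**Conclusion.** The rule is wrong as written and should be fixed. It discards a recorded month and year for the event that defines the primary endpoint, while neighbouring rules keep them. One Year 8 failure without a day would swap the Year 6 and Year 8 findings (0.31 and 0 instead of 0 and 0.43), add an event to the re-run 1-year and 2-year PIs, and lower the Kaplan-Meier failure rate to the end of Year 8 by 28-39%. The 3-year PI is essentially unaffected.

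These sizes rest on 350 women, 15% loss per year, no exposure removed for back-up contraception, and at least one partial conception date. The documents do not give the frequency of such dates; with none, nothing changes.

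**What to change.** Replace the conception-date sentence in SAP 4.3 with a rule of this kind: impute a partial conception date as the earliest date consistent with its recorded month and year; raise it to Day 1 Year 6 only if the recorded part allows that date; use Day 1 Year 6 outright only when nothing recorded places the conception. Then apply the existing counting rules of SAP 6.2.1, without forcing the imputed date into the window that ends 7 days after exposure. If only the year is known, the earliest date may still fall in the preceding treatment year; using the last negative pregnancy test as a lower bound is an optional refinement.

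For a missing removal day in a pregnant woman, state one rule for both the stop date and the PI. Applying the stop-date rule to the PI is the conservative choice, because it counts the pregnancy when the timing is uncertain.

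The cost is two sentences of SAP text and no new data. The Year 7 and 8 PIs and the Kaplan-Meier estimate may become less favourable, and the aligned removal rule may count a few conceptions that would be excluded if the removal day were known.
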